4.1. Overall Design

This study will test the hypothesis that **decreased abnormal hyperfunctional connectivity can be correlated with improved EM using a daily, low-dose LEV perturbation (AGB101 levetiracetam extended release)**. In this study, there are two study groups: APOE 4 carriers ($n=25$) and APOE4 noncarriers ($n=25$). The functional connectivity changes in HFC will be determined in a randomized, double-blind, placebo-controlled crossover manner, in which a low dose of AGB101 levetiracetam extended release (220 mg, QD) or placebo is administered to 50 healthy 55-75-year-old subjects (comprising 25 APOE 4 carriers and 25 noncarriers), with the order of treatments counterbalanced in a within-subject crossover design, as illustrated in

Fig. 2 below. The study procedures are almost identical to those described in Refs (77, 78). In brief, study participants will receive placebo during one treatment period and AGB101 levetiracetam extended release during the other treatment period, with the order of treatments counterbalanced (randomized, double-blind).

Figure 2. Study design and AGB101 treatment protocol

Notes: Of the 50 subjects, 25 are APOE 4 carriers and 25 are noncarriers.

See Table 1 for timing and schedule of procedures.

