5.4.7. Randomization, Study Drug Dispensation, Administration, and Compliance

The Investigational Drug Service at Froedtert Hospital will randomize participants to the treatment conditions.

In Period 1, all study participants will receive treatment with either AGB101 (220 mg, orally, QD) or placebo; in Period 2, all subjects will crossover and receive the other treatment. This is a double-blind study, so both the participants and study team will be blind to the treatment received.

All study treatments (drug and placebo) are dispensed in identical nondescript tablets by the Investigational Drug Service at Froedtert Hospital. Tablets are provided for daily morning doses. Study drugs will be dispensed at baseline and on the last day of the 4-week (-/+ 1 week) washout period. Subjects will be asked to self-administer treatment QD, once in the morning.

Treatment compliance will be monitored by participant self-report at the end of each treatment phase, bottle return and pill count, and analysis of AGB101 blood values at each visit during the study protocol.

Data Management

6.1. The Froedtert Hospital Investigational Pharmacy system will be used to enroll patients and obtain the randomly assigned treatment group. Data forms will be printed, completed, and entered into a database. The database will be monitored for completeness, consistency, accuracy, and timeliness. No patient-identifying information will be stored in the database. To ensure that data are secure from external violation, computer systems containing study data will be password protected, and physical access to the computer systems will be limited.

6.2. Determination of Changes in Network Activity and Concurrent Improvement in EM. The cognitive and MRI/rfMRI datasets will be obtained at baseline (before placebo/AGB101 administration) and on the last day of each 2-week treatment period. These two time points will be denoted $t = 1, 2$. The two 25-subject groups, both of which will receive both placebo and AGB101 at different treatment phase, will be denoted $g = 1, 2$. The set of EM scores for subject s , from group g , at time t will be denoted $Cog(s,g,t)$, where $s = 1, \dots, 25$; $g = 1, 2$; and $t = 1, 2$. The HFC calculated between the hippocampus and the bilateral sensorimotor cortex for subject s , from group g , at time t will be denoted $HFC(s,g,t)$.

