6.3. Functional-Connectivity Changes Due to Perturbation. We employed age, years of education, gender, and gray matter (GM) volume as time-invariant covariates to obtain residual variables to determine the HFC changes due to perturbation. We will model the HFC as a function of these nuisance regressors, using the following multiple linear regression equation, and retain the residuals as $HFC_{Res}^+(s, g, t)$ for further analysis:

$$HFC(s, g, t) = \beta_0 + \beta_1 Age(s) + \beta_2 Edu(s) + \beta_3 GM(s) + \beta_4 CSF(s) + \beta_5 Gender(s) + Res(s, g, t),$$

where $\widetilde{HFC}^+(s, g, t) \equiv Res(s, g, t)$. This regression will be performed using all of the data (i.e., all subjects, all groups, and all times). The GM measurement will be conducted with GM concentration and hippocampal volume measurement, as described in our publication and others (71-74). We will test the residuals $\widetilde{HFC}^+(s, g, t)$ using three-factor crossed-nested analysis of variance (ANOVA), with fixed factors of group and

time and a random factor of *subject* nested within *group* (i.e., all subjects will be tested at all times, but the placebo and AGB101groups will contain different treatment phases). We will test for both group and time main effects, as well as for the group \times time interaction. If we find significant main effects or interactions, we will perform post hoc procedures to determine which time and group (i.e., placebo vs. AGB101) combinations are significantly different. In addition to the HFC analysis, we will conduct a DMN analysis 75).

6.4. EM Changes Due to AGB101Perturbation. The two EM scores (AVLT and LMT) will be normalized to Z-score by transforming individual raw test scores according to the mean and standard deviation of the scores for all subjects. Then, Z-scores of each test will be averaged to obtain individual composite memory Z-score, as we have previously published (76). Similar to the above model for HFC changes due to AGB101perturbation, we will model the Cog score, using the time-invariant covariates as nuisance regressors:

$$\Delta EM(s, g, t) = \beta_0 + \beta_1 Age(s) + \beta_2 Edu(s) + \beta_3 GM(s) + \beta_4 CSF(s) + \beta_5 Gender(s) + Res(s, g, t)$$

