Define $\widehat{\Delta EM}(s, g, t) \equiv Res(s, g, t)$. We will test the residuals $\widehat{\Delta EM}(s, g, t)$ using a three-factor crossed-nested ANOVA, with fixed factors *group* and *time*, and random factor *subject* nested within *group*. We will test for group and time main effects, as well as the group \times time interaction. If we find significant main effects or interactions, we will perform post hoc procedures to determine which time and group combinations are significantly different.

6.5. Prediction of Changes in Correlation Between HFC and EM Before and After AGB101Perturbation. A multiple linear regression is used to model EM as a linear function of HFC and test the difference in slope and intercept between the AGB101and placebo groups. If the subject is in the AGB101group, $I(s, g) = 1$; if the subject is in the placebo group, $I(s, g) = 0$.

$$EM(s, g) = \beta_{0,0} + \beta_{0,1} I(s, g) + \beta_{1,0} HFC(s) + \beta_{1,1} HFC(s)I(s, g) + Res(s)$$

Here, **HFC(s)** represents baseline HFC for subject s (for simplicity, nuisance regressors are not shown).

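### Section 6.5 does not centre HFC, so its intercept test compares AGB101 with placebo at baseline HFC = 0 rather than at mean HFC

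*Protocol*

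**What the plan says.** Section 6.5 (protocol, repeated in the SAP) models EM with a treatment indicator I, coded 1 for AGB101 and 0 for placebo:

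EM = b00 + b01·I + b10·HFC + b11·HFC·I + residual

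The purpose is to "test the difference in slope and intercept between the AGB101and placebo groups". In this notation those are b11 and b01. The HFC term "represents baseline HFC for subject s (for simplicity, nuisance regressors are not shown").

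Four other places bear on how HFC enters the model:

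- Section 6.2 introduces the symbol as an unadjusted connectivity: "The HFC calculated between the hippocampus and the bilateral sensorimotor cortex for subject s".
- Section 6.3 builds a residualised HFC under a different, accented symbol and keeps it for later use. Of the regression behind it the plan says: "This regression will be performed using all of the data (i.e., all subjects, all groups, and all times"). Section 6.5 does not use that symbol.
- Section 6.4 standardises the memory outcome: "Z-scores of each test will be averaged to obtain individual composite memory Z-score". Nothing comparable is said of HFC.
- Section 4.1 gives the sample as "50 healthy 55-75-year-old subjects (comprising 25 APOE 4 carriers and 25 noncarriers"), each receiving both treatments.

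The plan does not say at which HFC value the intercept difference is to be read.

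**The concern.** Once a product term is in the model, the coefficient of treatment alone is the treatment difference where the other variable is zero. A reader of the results may well take b01 as the drug's effect on memory in a typical participant. As specified, it is that effect only under special conditions.

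The intercept is one of the two tests that Section 6.5 names, and the synopsis bases its efficacy assessment on the HFC-EM relationship that this section models. Unequal slopes are also a possibility the plan takes seriously. Section 6.5 tests for them, Section 3.3 reports faster EM decline with higher HFC in carriers, and Section 6.6 envisages high-HFC and low-HFC subgroups. If the slopes differ, b01 and the difference at mean HFC are different quantities. If they do not, b01 estimates the same quantity less precisely than it could.

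**Working it through.** The plan states no sample-size calculation, power or alpha for this analysis, so there is no figure to reproduce. The check is algebra plus illustration.

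**Inputs from the documents.** The model, coding and definition of HFC (Section 6.5); 50 subjects, each receiving both treatments (Section 4.1). **Assumed.** Mean and SD of baseline HFC, two-sided alpha of 0.05, effect sizes and residual SD. I also assume that each subject contributes an EM score under both treatments, so both conditions share the same baseline HFC values.

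**Step 1: what b01 is.** At HFC = h the AGB101-placebo difference is b01 + b11·h. At h = 0 this is b01; at mean HFC m it is b01 + b11·m. The two agree only if m = 0 or b11 = 0. Nuisance regressors that enter additively do not change this.

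**Step 2: precision.** Regress the within-subject difference in EM on HFC, with n subjects, error variance σ² and HFC standard deviation s:

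- variance of the difference at mean HFC = σ²/n
- variance of b01 = σ²/n + σ²·m²/(n·s²) = (σ²/n)(1 + m²/s²)

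The ratio of standard errors is sqrt(1 + r²), with r = m/s.

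**Step 3: range.** Suppose, for illustration, that an effect has 80% power when tested at mean HFC (z = 0.84 + 1.96 = 2.80) and the slopes are equal. Power for b01 is then Φ(2.80/sqrt(1 + r²) − 1.96).

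| r = mean/SD | SE factor | 2.80 / factor | Power |
|---|---|---|---|
| 0 | 1.00 | 2.80 | 80% |
| 0.5 | 1.12 | 2.50 | 71% |
| 1 | 1.41 | 1.98 | 51% |
| 2 | 2.24 | 1.25 | 24% |

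**Step 4: check by fitting.** In one simulated data set, b01 + b11 × mean HFC from the uncentred fit and b01 from the centred fit were both 0.18306. The slope test gave p = 0.1251 both ways.

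**Step 5: simulation.** 4,000 runs per setting; 50 subjects, 100 records, independent errors with SD 1, HFC SD assumed to be 0.15. Rejection rates for the intercept test:

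| Assumed mean HFC | Effect 0.5, equal slopes: uncentred / centred | No effect at mean HFC, slope difference −0.5 Z per SD of HFC: uncentred / centred |
|---|---|---|
| 0 | 0.69 / 0.69 | 0.05 / 0.06 |
| 0.1 | 0.52 / 0.69 | 0.28 / 0.06 |
| 0.2 | 0.30 / 0.70 | 0.50 / 0.06 |
| 0.3 | 0.19 / 0.70 | 0.57 / 0.06 |

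With no effect at any HFC value, both versions reject in about 5% of runs. In the last column the uncentred test is not in error about its own question. At mean 0.3, for example, the true difference at HFC = 0 is 0.5 × 0.3/0.15 = 1.0 Z. The rejection misleads only if it is read as an effect at average HFC.

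**The case against.** **The plan never says that b01 is the effect in an average subject.** Section 6.5 compares two regression lines, its title concerns the correlation, and EM change is handled in Section 6.4. This largely stands. As an intercept difference b01 is not biased, and centring leaves the slope test, the fitted lines and any joint slope-and-intercept test unchanged. But the intercept is named as a test in its own right, and the plan does not say where it is to be read.

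**Section 6.5 might use the residuals from Section 6.3.** Their mean over all data is zero, so the point would largely disappear. The text favours the other reading: the residual symbol is absent, and the remark that nuisance regressors are omitted from the display implies that they enter the 6.5 model directly. It is not certain, and the same clarifying sentence would settle it.

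**The difference at mean HFC can be obtained from the same fit at any time.** True. Nothing is lost irrecoverably; the gain is that the contrast is fixed in advance.

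**How far zero lies from the data.** Because the trial is about hyperconnectivity, a reader might infer that HFC = 0 lies at or beyond the edge of the observed range. The documents do not support that. They give no mean, SD, range or scale for HFC. Section 3.3 speaks of higher and lower HFC among carriers, which is relative. Half the sample are noncarriers, and no criterion in Section 4.2 selects on HFC.

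**Conclusion.** The point holds in a limited form. On the natural reading of Section 6.5, b01 is the AGB101-placebo difference in EM at baseline HFC = 0. It matches the difference at mean HFC only if mean HFC is 0 or the slopes are equal, and its standard error carries the factor sqrt(1 + mean²/SD²).

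The size cannot be fixed from the documents. It runs from nothing, if mean HFC is near 0, to 1.12, 1.41 or 2.24 times at assumed mean/SD ratios of 0.5, 1 or 2. A reader might take the power figures above as this trial's power. They are not: the 80% reference, the effect sizes and the HFC distribution are all assumed.

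Nor should a reader conclude that the trial's main result is at risk. The slope test and the primary analysis in Section 6.3 are untouched, and Section 6.6 already concedes that EM changes may not be detectable. Severity is minor. The change is still worth making, because centring at the mean of the analysed subjects is never less precise and is more precise whenever mean HFC is not 0.

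**What to change.** Add to Section 6.5 of the protocol and SAP: *HFC(s) is the unresidualised baseline value, centred at the Visit 1 mean of all subjects included in this analysis; b01 is the AGB101-placebo difference in EM at that mean and is interpreted together with b11.* If residuals were intended, say so instead. Testing b01 + b11 × mean HFC, with its confidence interval, is equivalent.

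Centring at the carriers' mean would not give a carrier-specific effect. The printed model pools both genotype groups and has no APOE term, so the result would be the pooled difference at that HFC value. A carrier-specific effect needs an APOE term or a fit in carriers alone.

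Cost: one sentence, with no new data and no change to the slope test.

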6.6. Expected Results, Deliverable, and Problems

Through this study, we expect to realize two goals: **Scientifically**, we will demonstrate that aberrant HFC represents a primary upstream mechanism that may contribute to cognitive deficits in CN APOE 4 carriers. Further, we will demonstrate that changes in the dysfunctional hippocampal network upon AGB101perturbation can be quantified as a biomarker for measuring network responses. **Clinically**, we expect that the short-term changes in network activity after the 2-week perturbation period will lead to a decrease in HFC, and possibly to cognitive improvement. This study can provide conceptual proof for preventive intervention. Using the predictive relationship between HFC and the EM changes, individuals carrying the APOE 4 allele can then be stratified into high and low HFC activity subgroups to further refine the subpopulation. Also, this study will provide information and address the power of adequate enrollment, protocol adherence, subject retention, and safety for future pilot trials.

We may be able to detect HFC changes in the 2-week period after AGB101perturbation as a primary outcome, but we may not be able to detect significant EM changes as the secondary outcome in this short R21 funding mechanism. In a future study, we could extend follow-up to 26 weeks or a year to enable us to detect the slowly declining EM functions.

7. DATA SAFETY MONITORING PLAN

An appointed DSMB will discuss the ethical conduct of the trial, review event definitions and the subject ICF form, and further develop plans for monitoring the data and safety of the trial. The DSMB will meet at least every six months to review the course of the trial and interim data. The DSMB agrees to communicate with institutional review board (IRB)/human subject committees to provide reassurances, as appropriate. There will be three DSMB members with the following areas of expertise:

- Neural mechanism underlining learning and memory in aging and neurological disease
- Aging and memory loss
- Psychology and neuroimaging

7.1. Safety Plan

The safety issues in this study are related to use of LEV and acquisition of fMRI data. This study uses the AGB101 levetiracetam extended release at a dose that is 10 times smaller than the doses typically used to treat epilepsy, the main indication for standard LEV. LEV is associated with rapid and complete absorption, high oral bioavailability, minimal metabolism, and primarily renal elimination. The LEV plasma half-life in adults is 7 ± 1 hour and is unaffected by either dose or repeated administration. LEV is eliminated from the systemic circulation by renal excretion as an unchanged drug, which represents 66% of administered dose. The total body clearance is 0.96 mL/min/kg and the renal clearance is 0.6 mL/min/kg. The mechanism of excretion is glomerular filtration with subsequent partial tubular reabsorption. The metabolite ucb L057 is excreted by glomerular filtration and active tubular secretion with a renal clearance of 4 mL/min/kg. LEV elimination is correlated to creatinine clearance. LEV clearance is reduced in patients with impaired renal function. It lacks cytochrome P450 isoenzyme-inducing potential and is not associated with clinically significant pharmacokinetic interactions with other drugs, including other antiepileptic drugs (55). Among AEs reported over placebo at standard therapeutic doses of 1000–2000 mg daily are pharyngitis (9%), mood swings (4%), dizziness (5%), infection (5%), asthenia (6%), and somnolence (7%). Serious dermatological reactions, including Stevens-Johnson syndrome and toxic epidermal necrolysis, have been reported in at 14–17 days from initiation of treatment.

7.1.1 Adverse Event Reporting

Throughout the course of the study, all AEs will be monitored and recorded on an AE CRF, including the AE's description, start and end date, outcome, seriousness, severity, action taken, and relationship to the study drug. If AEs occur, the first concern is the safety of the study subjects. All AEs will be followed until resolved or stable and the outcome documented on the CRF.

7.1.2 Definitions and Criteria

7.1.3 Adverse Events

Per International Conference on Harmonisation (ICH) E2A: An AE is any untoward medical occurrence in a subject or clinical investigation subject administered a pharmaceutical product and which does not necessarily have to have a causal relationship with this treatment. An AE can therefore be any unfavorable and unintended sign (including an abnormal laboratory finding, for example), symptom, or disease temporally associated with the use of a medicinal product, whether or not considered related to the medicinal product.

Events meeting the definition of an AE **include**:

- Exacerbation of a chronic or intermittent pre-existing condition including either an increase in frequency and/or intensity of the condition
- New conditions detected or diagnosed after investigational product administration even though it may have been present prior to the start of the study
- Signs, symptoms, or the clinical sequelae of a suspected drug interaction
- Signs, symptoms, or the clinical sequelae of a suspected overdose of either investigational product or a concomitant medication

Clinically significant abnormal findings (laboratory test results, vital signs, physical examination findings, ECGs, radiologic exams, or other studies) should be recorded as AEs. A "clinically significant" finding is one that affects clinical management, including additional visits, monitoring or referrals, diagnostic tests or alteration of treatment, or that is considered clinically significant by the investigator. A clinically significant finding may be a change in a test that has previously been abnormal but now requires additional action.

When a medical or surgical procedure is performed, the condition that leads to the procedure should be recorded as the AE.

Events that **do not** meet the definition of an AE include:

- Anticipated day-to-day fluctuations or expected progression of pre-existing disease(s) or condition(s) present or detected at the start of the study unless judged by an investigator to be more severe than expected for the subject's underlying condition
- Abnormal laboratory, ECG, or vital sign measurements that are not labelled clinically significant (see definition above)
- Situations where an untoward medical occurrence did not occur (social and/or convenience admission to a hospital)
- Pregnancy
- Overdose in the absence of other AEs will not be reported as an AE in its own right
- Changes in C-SSRS during the course of the study indicating worsening should be evaluated by the investigator for clinical significance, and if clinically significant (eg, alteration in medical care or intervention is required), an associated AE should be recorded, if present. The AE should be the primary underlying clinical manifestation assessed as clinically significant, and not the change in score itself.
- Change in cognitive functioning (improvement or worsening) is also not considered to be an AE.

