4.2. Inclusion and Exclusion Criteria

Inclusion Criteria

- Fluent in English
- At least eight years of education
- A Geriatric Depression Scale (GDS) (62) score < 6 and Hachinski Ischemic Score ≤ 4
- Normal general cognitive function as well as 1) normal memory function, documented by MOCA score of 23 or greater, and a RBANS Delayed Memory Index score of 85 or greater.

Exclusion criteria

- Neurological diseases, such as Parkinson's disease, multi-infarct dementia, Huntington's disease, normal pressure hydrocephalus, brain tumor, progressive supranuclear palsy, seizure disorder, subdural hematoma, multiple sclerosis, or a history of significant head trauma followed by persistent neurologic deficits or known structural brain abnormalities
- Presence of major psychiatric disease or chronic unstable medical conditions
- History of drug abuse
- History of alcohol abuse (4 or greater drinks per day on average)
- Contraindication to MRI
- Known clinically significant abnormalities in B12 or thyroid function tests
- End Stage Renal Disease (ESRD)
- Hemodialysis (HD)

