7.1.6 Reporting Procedures and Requirements

Adverse Events

AE recording will begin after the first dose of study drug is administered the morning after baseline. Thereafter, AEs will be ascertained by asking the subject how he/she has been since the last visit. Any AEs occurring before the start of treatment (ie, before the first dose of the study drug) will be recorded in the medical history only. If the investigator detects an AE in a study subject within 1 month (4 weeks, -/+ 1 week) of the last scheduled follow-up visit this will also be collected. All AEs will be followed until resolved or stable and the outcome documented on the CRF.

Also, the sign, symptom, or disease present before starting the treatment period are only considered AEs if they worsen after starting the treatment period.

The investigator should report all information about AEs on the AE/SAE section of the Case Report Form (CRF). Whenever possible, an AE will be reported using a diagnostic term (eg, “common cold” or “upper respiratory infection” rather than “runny nose, cough, mild fever”) and should be described with the attributes.

Serious Adverse Events

Each AE will be assessed to determine whether it meets seriousness criteria (Section 7.1.2.2). If the AE is considered serious, the investigator should report this event to Agene Biotech as outlined below and to the Institutional Review Board (IRB) & Data Safety Monitoring Board (DSMB) according to their standard operating procedures.

All information about SAEs will be collected and reported by entering the SAE information in the AE CRF. The investigator should send the initial report to the Site PI and to Agene Biotech within 24 hours of becoming aware of the SAE and followed by follow-up reports as soon as possible, whether the events are deemed related to the study drug or not. The information provided in the AE system should be as complete as possible, but minimally it must contain the following:

- Subject number
- Brief description of the SAE (diagnosis or signs/symptoms)
- Serious criteria
- Causality assessment
- Assessment of the intensity of the event

Agene Biotech will receive notification of the initial SAE via an e-mail from MCW Study Team. Site personnel will complete the paper SAE report form, scan and e-mail it within 24 hours to the following address: [contact]

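### Protocol Section 7.1.3 excludes all cognitive worsening from adverse events without the clinical-significance exception given to comparable items, contradicting its own AE definition

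*Protocol*

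**What the plan says.** Protocol Section 7.1.3 opens with a broad definition taken from ICH E2A: "An AE can therefore be any unfavorable and unintended sign (including an abnormal laboratory finding, for example), symptom, or disease". It adds that clinically significant abnormal findings, including those from physical examination and other studies, should be recorded as AEs. A finding counts as clinically significant if it affects management (extra visits, referrals, tests, altered treatment) or if the investigator judges it so.

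The section then lists what is not an AE. The last item reads: "Change in cognitive functioning (improvement or worsening) is also not considered to be an AE". Nothing in the item refers to severity, clinical significance or seriousness.

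Section 7.1.4 defines a serious adverse event (SAE) as an untoward medical occurrence with one of several outcomes, among them hospitalization and persistent or significant disability. It does not require the occurrence to be an AE first, and it does not repeat the cognitive exclusion. Section 7.1.6 sets the procedure: "Each AE will be assessed to determine whether it meets seriousness criteria".

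The SAP text available contains no AE definition that settles the matter.

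**The concern.** Subjects are healthy volunteers aged 55–75 who must show "Normal general cognitive function as well as 1) normal memory function" at entry (Section 4.2). They take a centrally acting drug for two weeks, and the Protocol Summary presents the study as the first to evaluate safety as well as efficacy in this population. New confusion or memory impairment on treatment is an event that safety surveillance should be able to see in an individual. As written, the last bullet tells site staff not to record it, while the definition earlier in the same section tells them to record it. If staff follow the bullet, the AE listing will understate cognitive harm by construction. If some follow the bullet and others the definition, recording will be inconsistent.

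**Working it through.** No statistical formula applies, so the check is a comparison of passages.

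**1. The exclusions in Section 7.1.3, side by side**

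| Item said not to be an AE | Exception kept |
|---|---|
| Fluctuation or expected progression of a pre-existing condition | Yes: "unless judged by an investigator to be more severe than expected" |
| Abnormal laboratory, ECG or vital-sign values | Yes: excluded only if not labelled clinically significant |
| Change in C-SSRS | Yes: "if clinically significant (eg, alteration in medical care or intervention is required), an associated AE should be recorded, if present" |
| Change in cognitive functioning | None |

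The remaining exclusions (social admission, pregnancy, overdose with no other AE) do not concern clinical worsening and are not comparable.

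**2. One case under each rule.** Suppose a subject reports new memory trouble in the second week and the investigator arranges an extra visit. There is no hospitalization and no lasting disability.
- AE definition: an unfavorable, unintended symptom in temporal association with the product, so an AE.
- Findings rule: an abnormality confirmed on examination or testing changed management, so it is clinically significant and should be recorded as an AE.
- Last bullet: a worsening of cognitive functioning, so not an AE.

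Staff cannot follow all three.

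**3. What depends on AE status**
- CRF recording and follow-up to resolution or stability (7.1.1)
- Intensity and relationship grading (under 7.1.5)
- The procedural seriousness check (7.1.6)
- DSMB review of AE frequency and severity, and the 5% threshold (7.6)
- The two-monthly analysis (7.8)

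Under the last bullet, the subject in step 2 contributes nothing to any of these.

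**4. The serious case.** Cognitive harm that led to hospitalization or disability would meet the definition in Section 7.1.4. The procedure in Section 7.1.6, however, starts from events already classed as AEs. It also cites Section 7.1.2.2 for the seriousness criteria. No such section exists, and the criteria are in 7.1.4. The route is unclear, but it is not closed.

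**5. Whether expected decline explains the exclusion.** Expected progression already has its own bullet, with an exception. Entry requires normal cognition, and each treatment period lasts 14 to 21 days (Table 1, note e). Section 6.6 treats memory decline as slow and suggests 26 weeks or a year of follow-up to detect it. Clinically evident worsening within two to three weeks cannot simply be put down to expected progression.

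**6. Whether the efficacy data fill the gap.** The neuropsychological battery is given at Visits 1, 2 and 4. Cognition is also reviewed at the 50% interim, under Efficacy (7.9), and the planned memory analysis (6.4) is a group ANOVA. Neither grades, attributes or follows an individual. At Visit 3 and at the telephone call four weeks after the last dose, AE enquiry is the only scheduled route in Table 1 for a cognitive complaint.

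**7. Illustration of leverage.** The denominator of the 5% threshold is not defined. If it counted subjects out of 50, then 0.05 × 50 = 2.5. Two subjects (2/50 = 4%) would not exceed it and three (3/50 = 6%) would. On that assumption, one unrecorded subject could decide whether it is crossed.

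**The case against.** The strongest counter-argument is that the bullet was meant narrowly. It follows the C-SSRS item, which ends by separating the underlying manifestation from the score, and it says cognitive change is "also" not an AE. Cognition is a study endpoint, and keeping endpoint scores out of the AE listing avoids double counting. That intention is plausible, but the text refers to functioning rather than to a test score, and it omits the clause that would give it the narrow meaning.

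Other objections stand and limit the point:
- A reader might infer that cognitive harm can never reach AE or SAE review. The documents do not support that. Section 7.1.4 stands on its own, and the findings rule in 7.1.3 pulls the other way. Section 7.10 has the DSMB address subjects' complaints, and Section 7.8 has the principal investigator notified of unexpected problems involving risk.
- Somnolence, dizziness, asthenia and mood swings (Section 7.1) are not changes in cognitive functioning and remain recordable. Their rates, given for 1000–2000 mg daily, cannot size what is missed here, and Section 7.1 lists no cognitive adverse effect.
- A reader might take Section 6.6 to mean that no memory change is expected. It says only that significant change may not be detected, and it allows for possible improvement.
- Cognition is not looked at only at the end: there is the 50% interim review, and early termination repeats the Period 2 assessments.

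**Conclusion.** The exclusion is wrong as written. It contradicts the AE definition and the findings rule in the same section, and it sits ambiguously with Sections 7.1.4 and 7.1.6. Non-serious but clinically evident cognitive worsening can go unrecorded as an AE in any of the 50 subjects, and serious cognitive harm has no clear procedural route. The conclusion rests on staff applying the bullet as it reads. The documents give no rate of cognitive worsening on this drug and dose, so no count of missed events can be supported. The 4% versus 6% comparison only illustrates leverage under an assumed denominator. The primary connectivity estimate and its test are not affected; the defect lies in safety capture.

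**What to change.** Reconcile the last bullet of Section 7.1.3 with the definition and findings rule above it and with Sections 7.1.4 and 7.1.6, using wording parallel to the C-SSRS item. For example: a change in a cognitive test score alone is not an AE; worsening of cognition that is clinically significant as defined in Section 7.1.3, or that meets a seriousness criterion in Section 7.1.4, is recorded as an AE under its underlying clinical manifestation. In the same amendment, correct the reference in Section 7.1.6 from 7.1.2.2 to 7.1.4.

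The cost is one sentence and one cross-reference in a protocol amendment. No new visit or test is needed, because the battery and the AE enquiries are already scheduled. The downside is a few more AE entries.
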